2B1	Users satisfaction on functioning on the Rheo knee 4/Navii in stair descent is no worse compared to hydraulic MPKs	
Self report: Modified PEQ ampulation subscale (item 13D)
 
Please rate how you felt about being able to walk down stairs when using your prosthesis/the test prosthesis?
 
1=cannot, 10=No problem
	Rating (1-10)	
No worse rating compared to prescribed hydraulic MPK
 
89% $HDI_{low} \geq 0$ $pd > 97,0\%$ $ROPE < 2,5\%$)

2B2	Users satisfaction on functioning on the Rheo knee 4/Navii in stair descent is improved compared to Rheo Knee 3	Self report: Modified PEQ ambulation subscale (item 13D) Please rate how you felt about being able to walk down stairs when using your prosthesis/the test prosthesis? 1=cannot, 10=No problem	Rating (1-10)	Improved rating compared to prescribed magentorheologic MPK $(89\% HDI_{low} \geq 0$ $pd > 97,0\%$ $ROPE < 2,5\%$
-----	--	---	---------------	--

• Design of the Clinical Investigation

• General

The test will be a non-randomized single group open label prospective repeated measures (ABA) design.

Amputees are a small proportion of the general population. The population group specified in the inclusion/exclusion criteria is a further subsample of amputees. For practical reasons, i.e. to achieve statistical power, it is therefore more feasible to use within-subject comparison rather than creating study arms to compare. Furthermore, as mobile amputees generally have and use a prosthetic device for their daily activities, within-comparison is feasible comparing to the subject's previous device.

All investigational activities will be conducted at prosthetic out-patient clinics.

As stated above the primary endpoint is Satisfaction on descending stairs, see Table 5, and the secondary endpoints are satisfaction on descending ramps, balance confidence and standing comfort in that respective order of significance. In addition, there are two exploratory endpoints on mobility and balance during ambulation. See previous chapter on objectives and hypothesis and Table 5 for rationale.

Drop-outs and withdrawals may be replaced if deemed necessary to fulfil the methodological standards of the study.

Instruments for data collection will include the following:

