For Phase I, 17 subjects are to be enrolled and therefore **20** investigational devices will be used, as the devices are intended to be used by a single patient; one for each subject. The number of 20 investigational devices includes replacement units in case of failure.

For Phase II, the number of investigational devices will depend on the sample size, which will be determined using data from phase I.

● Subjects

All subjects will be dispositioned as follows:

- Screen Failure: Subject did not pass screening procedures, not called in for clinical visit;
- Candidate for enrollment: Passed screening procedures, accepts to come in for clinical visit;
- Enrolled: Subject signs informed consent and takes part in the first experimental session;
- Fitted: Subject leaves the clinic on the investigational device;
- Drop-out: Enrolled subject whose participation ended because they did not want to continue participation.
- Discontinued: Candidate for enrollment or Enrolled subject whose participation ended because they withdrew consent, were withdrawn by the Investigator, were lost to follow up, or died.

Table 7 Inclusion/Exclusion criteria

Inclusion: Only patients with the following characteristics are eligible for study entry:	Exclusion: Patients with the following characteristics are not eligible for study entry:
-45Kg < body weight < 136Kg	-Users with stump pain*
-Cognitive ability to understand all instructions and questionnaires in the study;	-Users with socket problems**
-Unilateral TF/KD amputees that are regular prosthesis users for at least 3 months	-Pregnant Users
-Current MPK users (passive MPKs only)	-Users using Power Knee, Kenevo or mechanical knees as their prescribed prosthesis
-Age \geq 18 years	-Alignment that cannot be matched with the Rheo Knee 4 setup, as described in Instructions for use.
-Willing and able to participate in the study and follow the protocol	-Osseointegration
-Moderate to high active users (PLUS M T-score > 40 ²¹)	

*Question on pain affecting their functional ability (yes/no)

**Socket fit: Socket fit comfort score over 5

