A subject can withdraw from participation at any time, at his/her discretion, and this will not have any consequences for the participant's treatment. In such cases a report stating reasons for discontinuation of the participant shall be prepared by the LPI. No further investigational procedures concerning the subject will be conducted, except for a statement explaining the reason for withdrawal, including but not limited to: interacting or interviewing the subject in order to obtain data on him/her; obtaining additional private information on the subject by either observing the subject or collecting or receiving such information from any source.

The LPI can withdraw the participant from the trial at any time. The reasons shall be documented. There are no pre-specified criteria for discontinuation of participants from the trial. The discontinuation of participants in the trial may result in replacement with new participants. If withdrawal is due to problems related to the investigational device the participant will be asked for permission to follow the status/condition outside the clinical investigation. The follow-up will be individualized.

Subjects will be enrolled at the clinic, the investigational site that they were contacted from.

The total time period required to implement the clinical investigation (**phase I**) is expected to be **8 weeks**. Each individual subject is expected to participate in the clinical investigation for **5 weeks**. The estimated time needed to include this number (enrolment period) is **2 weeks**.

The estimated time period needed to implement **phase II** will depend on the number of subjects needed for that phase, but it is anticipated it will take around **8-10 weeks**.

14 subjects are required to finish the protocol for statistical data analysis, as specified in chapter 10.2 Sample size calculation.

- **Procedures**

- i) Recruitment**

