Repeated measures analysis has the advantage of increased power vis-à-vis group allocations and reduction in error variance associated with individual difference, as each subject acts as its own control. This is important for studying amputees as the group is a small proportion of the total population, and with specific inclusion/exclusion criteria the total eligible population becomes very small, making it difficult to find and recruit subjects to attain an acceptable level of power. This limited population pool often results in slightly heterogeneous sample, as the amputees available are few and far between, in every sense. Furthermore, no single amputation procedure and therefore amputated stump is exactly the same, making the experience of each amputee a bit unique. The within-subject design significantly reduces the individual differences when comparing the two conditions.

The drawback of the design is the potential of “carryover effects”, i.e. experience from one condition can affect outcome or performance in the other condition, creating a confounding extraneous variable that varies with the independent variable. Such effects are: practice, positive carryover effect to the latter condition; and fatigue, negative carryover effect to the latter condition.

● Sample size calculation

[REDACTED]

Total sample size = 14
Actual power = 0.9600638

It is therefore expected that **14** subjects are required to complete the protocol with a power of **0,95** and significance at **0,05**. Effect size was estimated based on previous in-house studies on the previous version of the product for the primary end-point.

Given a drop-out rate of **20%**, **17** subjects will be recruited.

For pass/fail criteria, see Table 4 **Endpoints, test methods and hypotheses**.

Phase II:

Sample size calculations for phase II will be done using data from phase I.

• Additional statistical matters

There is no criteria for early termination of the clinical investigation on statistical grounds.

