Any deviations from the statistical plan provided in this protocol will have to be approved by the sponsor and the reasons for the deviation reported in the clinical investigational report. Drop-outs and withdrawn participants will be included in the data analysis for the procedures that they completed. They will be grouped together and compared to the group that finished the protocol. Any statistical differences of the two groups will be reported. If the participants have not provided any data, they will not be included in the data analysis. No particular information will be excluded from the statistical analysis and tests, as described above.

• Amendments and Deviations from the Protocol (CIP)

• Amendments

Any amendments to this protocol must be first approved by the sponsor and PI, and then be evaluated by the overseeing IRB and, where appropriate regulatory authorities, before being implemented.

For non-substantial changes (e.g. minor logistical or administrative changes, change of monitor(s), telephone numbers, renewal of insurance) not affecting the rights, safety and well-being of human subjects or not related to the clinical investigation objectives or endpoints, a simple notification to the IRB and, where appropriate, regulatory authorities can be sufficient.

• Deviations

Investigators are not allowed to deviate from this protocol without a formal approval from the IRB, if the deviation affects subject's rights, safety and wellbeing, or the scientific integrity of the clinical investigation. Any such deviation from the protocol is to be documented in detail and the report sent to the IRB.

Under emergency circumstances, deviations from the protocol to protect the rights, safety and well-being of human subjects may proceed without prior approval of the sponsor and the IRB. Such deviations shall be documented and reported to the sponsor and the IRB as soon as possible.

Investigators can request for an approval from the sponsor for a deviation if the deviation does not affect subject's rights, safety and wellbeing, or the scientific integrity of the clinical investigation.

In case of a deviation from this protocol taking place without prior approval from the sponsor, and IRB as applicable, it shall be reported to the sponsor within 24 hours of LPI knowledge of the deviation. The LPI responsible for the deviation is to send a report to the sponsor no later than five days after the deviation was reported. The report shall include:

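### Section 10.2: 17 recruits with 20% drop-out give 13.6 expected completers, not the 14 required; dividing by retention gives 18

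*Combined protocol and SAP*

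**What the plan says.** Section 10.2 (Sample size calculation) says that "14 subjects are required to complete the protocol with a power of 0,95 and significance at 0,05", with the program output line "Actual power = 0.9600638". The calculation block above it is redacted, so the test and the effect size cannot be seen. The section then sets recruitment: "Given a drop-out rate of 20%, 17 subjects will be recruited". It shows no inflation formula.

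The two numbers recur elsewhere. The Subjects section says that "14 subjects are required to finish the protocol for statistical data analysis". The section on the investigational device and comparators says "For Phase I, 17 subjects are to be enrolled and therefore" and provides 20 devices, replacement units included. The Summary also gives 17 for Phase I.

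Three statements bear on what happens when subjects are lost:

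- Design of the Clinical Investigation, General: "Drop-outs and withdrawals may be replaced if deemed necessary to fulfil the methodological standards of the study".
- Subjects: "The discontinuation of participants in the trial may result in replacement with new participants".
- Additional statistical matters: "Drop-outs and withdrawn participants will be included in the data analysis for the procedures that they completed".

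**The concern.** A drop-out rate is normally read as the share of recruited subjects who do not finish. On that reading the recruitment figure is the required number of completers divided by the proportion retained. Seventeen is what results from adding 20% of the completers instead, which is a common slip and always gives too small a number.

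What is at stake is whether the plan carries the allowance it claims. Section 10.2 makes the 14 a requirement for completion, and 17 recruits are expected to fall just short of it at the plan's own drop-out rate. The requirement is small and the section itself describes recruitment from this population as difficult, so the allowance should be stated accurately. The number also drives enrolment and the supply of devices.

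**Working it through.** **Inputs.** Required completers 14, drop-out 20%, recruits 17, alpha 0.05, target power 0.95 and actual power 0.9600638 at n = 14 (all Section 10.2); 20 devices (Investigational Device(s) and Comparator(s)).

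**Reproducing the plan's figure.** n × (1 + d) = 14 × 1.2 = 16.8, rounded up to 17. This matches. That it was the method used is an inference: rounding 17.5 down would also give 17.

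**Inflating by retention.** n/(1 − d) = 14/0.8 = 17.5, rounded up to 18.

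**Expected completers.** 17 × 0.8 = 13.6; 18 × 0.8 = 14.4. Seventeen recruits leave 14 completers only if at most 17 − 14 = 3 are lost, and 3/17 = 17.6%.

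**Chance of reaching 14.** Assume independent losses at 20% and no replacement, so that completers follow Binomial(N, 0.8).

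| Recruits | Mean completers | P(at least 14) | P(at least 13) |
|---|---|---|---|
| 17 | 13.6 | 0.549 | 0.758 |
| 18 | 14.4 | 0.716 | 0.867 |

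With 17 recruits the median and the mode are both 14.

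**Effect on power.** The test and effect size are redacted, so I assume a paired t-test and solve for the standardised effect that gives power 0.9600638 at n = 14 and alpha 0.05 (noncentral t). Average power is the sum over x of P(x completers) × power(x).

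| | One-sided | Two-sided |
|---|---|---|
| Implied effect size | 0.960 | 1.075 |
| Power, 14 completers | 0.9601 | 0.9601 |
| Power, 13 completers | 0.9465 | 0.9443 |
| Power, 12 completers | 0.9287 | 0.9228 |
| Average power, 17 recruits | 0.9497 | 0.9472 |
| Average power, 18 recruits | 0.9598 | 0.9590 |

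These figures describe the assumed t-test. They do not describe the Bayesian acceptance rule in the section on statistical design and procedures.

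**Timing of losses.** A subject lost after visit 2 still supplies a baseline and an investigational-device measurement. The plan does not say when losses are expected, so these are scenarios for 17 recruits:

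- All losses before visit 2: pairs follow Binomial(17, 0.8), and P(at least 14 pairs) = 0.549.
- Half before visit 2: pairs follow Binomial(17, 0.9), with mean 17 × 0.9 = 15.3 and P(at least 14 pairs) = 0.917.
- None before visit 2: all 17 supply a pair, and the probability is 1.

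**The case against.** The best defence is that 17 does follow from 14 and 20% if the 20% is read as a margin added to the completers, and Section 10.2 does not say which base it uses. The gap before rounding is half a subject (17.5 against 17). The mean of 13.6 is also set against a whole-number requirement, while the most likely outcome with 17 recruits is exactly 14 completers. The plan has other cushions too: replacement is allowed, partial data are analysed, and the test procedure foresees three sites with 4 to 10 users each (12 to 30 in all), so 17 is not a ceiling on capacity. On the assumed t-test, average power stays within 0.003 of the 0.95 target.

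Most of this stands as a statement about size, and it is why the point is minor. It does not reconcile the figures. The plan calls the 20% a drop-out rate, which is a share of those who enter, and 17 does not absorb a loss of that share. Both replacement statements are permissive, and neither commits to reaching 14 completers. Partial data help the comparison of baseline with the device, but the plan states its requirement in subjects who complete the protocol, and the design includes a third visit on the prescribed knee. Room at the sites does not alter the stated recruitment number.

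**Conclusion.** The concern holds, as a minor arithmetic correction. Seventeen recruits carry an allowance of 17.6%, not 20%, and the figure that matches 20% is 18. This part needs no redacted input.

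The consequence is one subject. Without replacement and with independent losses, the chance of having 14 completers is 55% instead of 72%. The cost in average power is about 0.01 (0.950 against 0.960 one-sided, 0.947 against 0.959 two-sided), conditional on the assumed paired t-test. If some losses come after visit 2, or drop-outs are replaced, the shortfall shrinks or disappears. The figure of 14 could not be checked, because its inputs are redacted; that is not a fault of the plan.

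**What to change.** Restate the sentence in Section 10.2 so that it says 17 subjects allow for 3 drop-outs (17.6%). Nothing in the conduct of the trial changes.

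If the 20% assumption is to be kept, set recruitment at 18 and carry it to the Summary and to the section on the number of devices. This costs one more subject, and the 20 planned devices then leave 20 − 18 = 2 spares instead of 20 − 17 = 3. A further option is to keep 17 and turn the permission to replace drop-outs into a commitment to recruit until 14 have completed.

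Either route passes through the plan's amendment procedure. The wording correction is nearly free and may need no more than notification to the IRB if it is judged non-substantial. A change in the number of subjects may need IRB evaluation.
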